5.1. Study Drug Information

Voxelotor is synthetic small molecule bearing the chemical name 2-hydroxy-6-((2-(1-isopropyl-1H-pyrazol-5-yl) pyridin-3-yl) methoxy) benzaldehyde. The chemical formula is C19H19N3O3 and the molecular weight is 337.38.

Amendment 3

Voxelotor 300 mg or 500 mg tablets contain GBT440 drug substance along with several formulation excipients. All the excipients used for the formulation are compliant with European regulations and are listed in the Food and Drug Administration (FDA) Inactive Ingredients Database (IID).

Voxelotor tablets will be supplied to clinical sites in high density polyethylene (HDPE) bottles with induction sealed polypropylene (PP) caps. Additional details are provided in the Pharmacy Manual.

All study medication will be stored at controlled room temperature between 15°C to 25°C, in the storage area of the investigational site pharmacy.

No special procedures for the safe handling on voxelotor are required. The Sponsor will be permitted upon request to audit the supplies, storage, dispensing procedures and records.

5.2. Study Drug Dispensation

Study Drug will be dispensed at the Day 1 visit and every 3 months thereafter. Participants will receive a 3-month (90 day) supply of study drug at each dispensation visit.

Participants should be instructed to take study drug once daily with water or other nonalcoholic beverage preferably at the same time each day. Study drug may be taken with or without food.

5.3. Drug Accountability and Retention

In accordance with Good Clinical Practice (GCP), the Investigational Site will account for all supplies of voxelotor. Details of receipt, storage, dispensation, and return will be recorded.

The Investigator must ensure that all drug supplies are kept in a secure locked area with access limited to those authorized by the Investigator.

The Investigator (or designee) will maintain an accurate record of the receipt of the investigational product as shipped by the Sponsor (or designee), including, but not limited to, the date received, storage conditions/location, lot number, amount received, and the disposition of all investigational product. A copy of the receipt will be returned to the Sponsor when the contents of the investigational product shipment have been verified.

Current dispensing records will also be maintained including the date and amount of investigational product dispensed and the participant receiving the drug. This drug accountability record will be available for inspection at any time.

At the completion of the study, the original drug accountability record will be available for review by the Sponsor upon request.

All unused supplies of voxelotor will either be destroyed by the investigational site or returned to the Sponsor in accordance with Sponsor instructions.

Additional details are provided in the Pharmacy Manual.

5.4. Dose Modification

Participants should adhere to the assigned dose. However, dose modification for management of adverse events should be considered as outlined below. Guidelines for reduction, interruption, or permanent discontinuation of study drug are provided below in Table 2 (study drug-related AEs) and Table 3 (study drug-related rash).

All instances of study drug modification (dose reduction, interruption, or discontinuation) are to be captured in the participants' medical record and on the CRFs. If the conditions/event leading to the dose modification have resolved, the original dose level may be resumed, unless in the judgment of the Investigator, this cannot be done safely.

If a participant enrolled in this study is on a reduced dose due to an AE prior to dose selection on GBT440-031, dosing may be continued at the reduced dose if deemed clinically appropriate by the Investigator.

Table 2. Dose Modification Guidelines for Study Drug-Related Adverse Events

Dose Reduction				
Event	Recommended Action			
Grade 2 or higher AE that is (1) study drug- related in the opinion of the Investigator AND (2) that precludes continued dosing at the current dose level due to safety concern or lack of tolerability (in the Investigator's judgment)	Study drug: May be reduced by one (1) tablet. If, in the opinion of the Investigator, a Grade 2 AE has resolved to ≤ Grade 1, participant may resume study drug at the original dose. If, in the opinion of the Investigator, the AE poses a significant safety concern such that a dose hold is considered, the Investigator may consider a dose interruption (hold), Maximum dose hold is 5 continuous days. If, in the opinion of the Investigator, a longer dose hold is clinically needed, the Medical Monitor should be contacted for discussion.			
ALT ≥3x ULN if ALT WNL at baseline OR >3X ULN AND a ≥2-fold increase above baseline values if elevated ALT values at baseline In the absence of additional signs of compromised liver function such as elevated	Study drug: Confirm by repeat testing within 48 to 72 hours if possible, then repeat liver panel at least weekly until ALT levels improves. Additional Actions: If ALT levels continue to increase reduce by one tablet and notify the Medical Monitor			

Table 2. Dose Modification Guidelines for Study Drug-Related Adverse Events

Dose Reduction	
Event	Recommended Action
PT, PTT, INR, elevated conjugated bilirubin, jaundice, or hepatic pain.	
ALT ≥5× and <8× ULN (confirmed by repeat testing within 48 to 72 hours) In the absence of additional signs of compromised liver function such as elevated PT, PTT, elevated conjugated bilirubin, jaundice, or hepatic pain.	Study drug: Reduce dose by one tablet. Additional actions: Repeat liver panel test within 48 to 72 hours if possible and then at least weekly until resolution to <5× ULN; if ALT test does not improve within 2 weeks of dose reduction, the Medical Monitor should be notified. If ALT continues to increase within 1 week after a dose reduction, dose should be interrupted, and the Medical Monitor should be notified.
Dose Interruption (Hold)	D 114.6
Event	Recommended Action
Grade 3 or higher AE that is (1) study drug - related in the opinion of the Investigator AND (2) that precludes continued dosing at the current or at a reduced dose level due to safety concern or lack of tolerability in the Investigator's judgment	Study drug: Hold dose until ≤Grade 2, then resume study drug at original dose. If, in the opinion of the Investigator, dosing should be resumed at a lower dose, contact the Medical Monitor. If the AE recurs or worsens, reduce dose by one tablet. Maximum dose hold is 5 continuous days. If, in the opinion of the Investigator, a longer dose hold is clinically needed, the Medical Monitor should be contacted for discussion.

Table 2. Dose Modification Guidelines for Study Drug-Related Adverse Events (Continued)

Drug Discontinuation	
Event	Recommended Action
Grade 3 or higher, study drug-related SAE	Study drug: Discontinue study drug. If the Investigator considers that the participant would benefit from continuing treatment, the Medical Monitor should be contacted for discussion.
Grade 3 or higher study drug-related AE that, at the discretion of the Investigator, warrants discontinuation of study drug (eg, has not improved or resolved after dose hold)	Study drug: Discontinue study drug. If the Investigator considers that the participant would benefit from continuing treatment, the Medical Monitor should be contacted
Consider treatment discontinuation if:	Study drug: Hold dose, confirm by repeat testing within 48 to 72 hours if possible, and assess for

Table 2. Dose Modification Guidelines for Study Drug-Related Adverse Events (Continued)

Drug Discontinuation	
Event	Recommended Action
ALT >8× ULN (1) ALT >3x ULN or (2) ALT≥3x AND ≥2-fold increase above baseline values if elevated ALT values at baseline with additional signs of compromised liver function such as elevated PT, PTT, INR, elevated conjugated bilirubin, jaundice, or hepatic pain, appearance of fatigue, nausea, vomiting, right upper	potential reversible causes of liver function test abnormalities. Contact the Medical Monitor for discussion of study drug discontinuation.
quadrant pain or tenderness, fever, rash, and/or eosinophilia	

Table 3. Dose Modification Guidelines for Study Drug-Related Rash

Dose Reduction	
Event	Recommended Action
Grade 1 or 2 study drug-related rash	Management: Consider antihistamines, topical steroids as clinically indicated.
	Study drug: If rash does not resolve or improve to Grade 1 within 4 days after oral antihistamines and/or topical steroids, the dose may be reduced by one (1) tablet. The dose may be reduced further by one tablet if the event does not resolve.
	If in the opinion of the Investigator, a Grade 2 AE has resolved to ≤Grade 1, participant may resume study drug at the original dose.
Dose Interruption (Hold)	
Event	Recommended Action
Grade 1 or 2 study drug-related rash that persists after dose reduction	Management: Consider antihistamines, topical steroids as clinically indicated. Consider a Dermatology Consult if clinically indicated.
	Study drug: If rash does not resolve or improve to Grade 1 on the lower dose, consider a dose hold until resolution or event returns to Grade 1 or Baseline. Once rash has resolved or improved to Grade 1, dosing may be resumed at the

Table 3. Dose Modification Guidelines for Study Drug-Related Rash

Dose Reduction	
	reduced level. Maximum dose hold is 5 continuous days. If, in the opinion of the Investigator, a longer dose hold is clinically needed, the Medical Monitor should be contacted for discussion.
	If, in the opinion of the Investigator, a Grade 2 AE has resolved to <grade 1,="" at="" dose.<="" drug="" may="" original="" participant="" resume="" study="" td="" the=""></grade>
Drug Discontinuation	
Event	Recommended Action
Grade 3 or higher study drug-related rash	Study drug: Discontinue study drug. Consider a Dermatology Consult if clinically indicated. Notify Medical Monitor.

5.5. Concomitant Medications

A concomitant medication is defined as any prescription or over-the-counter preparation, including vitamins and supplements, as well as investigational products other than those under study in this trial.

5.5.1. Prior and Concomitant Medications

Except as noted below, in the interests of participant safety and acceptable standards of medical care, the Investigator will be permitted to prescribe treatment(s) at his/her discretion. All administered concomitant medications from signing the ICF until 28 days after the participant's last dose of study drug must be recorded on the participants' CRF (medication, dose, treatment duration and indication).

5.5.2. Allowed Concomitant Medications

Permitted concomitant medications include penicillin, folic acid, and codeine, which are among the chronic medications commonly taken by SCD participants.

Hydroxyurea (HU), L-glutamine therapy and crizanlizumab, where available, are allowed.

5.5.3. Prohibited Medications

Use of an investigational product other than that under study in this trial, regardless of its intended use, is prohibited throughout the trial and for the 28 days after the last dose.

Voxelotor is a moderate CYP3A4 inhibitor and should not be co-administered with sensitive CYP3A4 substrates with a narrow therapeutic index. See Table 4 for examples.

090177e19fbdcff7\Approved\Approved On: 24-Jan-2024 21:35 (GMT)

Table 4. Sensitive CYP3A4 Substrates with Narrow Therapeutic Range

Sensitive CYP3A4 Substrates with Narrow Therapeutic Range	
Alfentanil, sirolimus, and tacrolimus	

Amendment 3

Please note the following: This is not an exhaustive list. Country-specific lists may be used if available.

Since CYP3A4 is a primary CYP (cytochrome P450) responsible for the metabolism of voxelotor, concomitant use of voxelotor and moderate or strong inducers of CYP3A4 is not allowed (refer to Table 5 for examples).

Table 5. Examples of Moderate and Strong CYP Inducers

CYP3A4	Examples
Moderate CYP3A4 Inducers	Cenobamate, dabrafenib, bosentan, efavirenz, etravirine, lorlatinib, pexidartinib, phenobarbital, primidone, and sotorasib
Strong CYP3A4 Inducers	Apalutamide, carbamazepine, enzalutamide, ivosidenib, lumacaftor, mitotane, phenytoin, rifampin, and St. John's wort

Please note the following: This is not an exhaustive list. Country-specific lists may be used if available. For an updated list, refer to the following link:

https://www.fda.gov/Drugs/DevelopmentApprovalProcess/DevelopmentResources/DrugInteractionsLabeling/ucm093664.htm#table3-3. (last accessed 30 March 2023).

Medications listed in Table 6 are also prohibited.

Table 6. Additional Prohibited Medications

Prohibited Medications	
Cisapride	

This list of drugs prohibited for potential DDI concerns with the IMP may be revised during the course of the study with written notification from the sponsor to include or exclude specific drugs or drug categories for various reasons (eg, emerging DDI results for the IMP, availability of new information in literature on the DDI potential of other drugs) if the overall benefit/risk assessment is not impacted or if the changes do not significantly impact the safety of participants or the scientific value of the trial.

5.5.4. Management of Overdose

Based on the mechanism of action of voxelotor, an overdose might decrease O₂ delivery to tissues. Transfusion, exchange transfusion, and/or hyperbaric O₂ therapy may be administered in the event of a medical emergency due to a suspected voxelotor overdose.

5.6. Fertility/Contraceptive Requirements

There is no information about effects that voxelotor could have on the development of the fetus in humans. Therefore, all female participants of child-bearing potential (post menarche) should avoid pregnancy, and all active male participants should avoid fathering a child. Highly effective means of contraception are listed below in Section 5.6.4.

5.6.1. Instructions for Female Participants of Child-Bearing Potential

For female participants of child-bearing potential, pregnancy should be avoided by either abstinence from sex/sexual intercourse or the use of highly effective means of contraception for the duration of the study, and for a total period of 30 days after the participant has taken her last dose of voxelotor. Pregnancy reporting requirements are outlined in Section 7.2.4.

5.6.2. Female Participants of Non-Child-Bearing Potential

Female participants of non-child-bearing potential are defined as: pre-menarche, bilateral oophorectomy/ hysterectomy/ post-menopausal females being amenorrhoeic for greater than 2 years with an appropriate clinical profile, eg, age appropriate, history of vasomotor symptoms.

5.6.3. Instructions for Male Participants

It is important that the partners of male participants do not become pregnant during the study and for a total period of 30 days after the male participant has taken their last dose of voxelotor.

As a precaution, all male participants should avoid fathering a child by either abstinence or the use of barrier methods of contraception. As there is no information for voxelotor being secreted in the ejaculate, male participants (including men who have had vasectomies) whose partners are currently pregnant should use barrier methods for the duration of the study and for 30 days after the last dose of voxelotor.

5.6.4. Acceptable Forms of Contraception

Highly effective methods of birth control are defined as those which result in a low failure rate (i.e., less than 1% per year) when used consistently and correctly. Highly effective methods of birth control are as follows:

- Combined (estrogen and progestogen containing) hormonal contraception associated with inhibition of ovulation:
 - Oral
 - Intravaginal
 - Transdermal
- Progestogen-only hormonal contraception associated with inhibition of ovulation:
 - Oral

- Injectable
- Implantable
- Hormonal contraception must be supplemented with a barrier method (preferably male condom)
- Intrauterine device (IUD)
- Intrauterine hormone-releasing system (IUS)
- Bilateral tubal occlusion
- Sexual abstinence: Sexual abstinence is considered a highly effective method only
 if the participant is refraining from heterosexual intercourse during the entire
 period of risk associated with the study treatments. The reliability of sexual
 abstinence needs to be evaluated in relation to the duration of the clinical trial and
 the preferred and usual lifestyle of the participant.

For male participants with female partners capable of reproduction: barrier methods of contraception: condom or occlusive cap (diaphragm or cervical/vault caps) with spermicidal foam/gel/film/cream/suppository. The use of barrier contraceptives should always be supplemented with the use of a spermicide.

5.7. Treatment Compliance

Treatment compliance will be based on comparison of the dispensed versus returned study drug.

5.8. Randomization and Blinding

This is a non-randomized, open-label study of voxelotor.

6. ASSESSMENT OF TREATMENT EFFECT

The durability of the reduction of hemolysis will be assessed by hematological parameters. Hematology assessments for this trial are described in Section 7.1.5.1.

7. ASSESSMENT OF SAFETY

7.1. Safety Parameters

Participant safety and tolerability will be monitored during the study using standard measures, including physical examinations, vital signs (including blood pressure [BP]), safety laboratory tests, concomitant medication usage and AE monitoring. Assessments will be performed at defined times during the study as indicated in the Schedule of Assessments (Appendix 1).

There are additional assessments (Week 4 and Week 8) during the first 8 weeks of this study for participants who transition from GBT440-031 and meet the following criteria:

- If the dose for this trial is 1500 mg, and the participant was randomized to either voxelotor 900 mg or placebo in GBT440-031.
- If the dose is 900 mg, and the participant was randomized to placebo in GBT440-031 study.
- If a participant received less than 12 weeks of treatment in GBT440-031.

More frequent assessments, as per Investigator or health care provider judgement, may be conducted if needed for management of AEs or per standard of care at each site.

7.1.1. Demographic/Medical History

Medical history will be recorded at the time of the physical examination on Day 1. The medical history will include information captured under Study GBT440-031 and new events that occurred since participating in GBT440-031 as clinically appropriate. Ongoing AEs in GBT440-031 will be recorded as new Medical History for this trial.

7.1.2. Vital Signs

Vital signs (heart rate [HR], BP) will be collected after a participant has rested for at least 5 minutes in the seated or supine position. A repeated measurement of HR and BP will be taken if the first reading is outside the normal range and deemed clinically significant.

7.1.3. Physical Examination

An abbreviated PE and a symptom directed examination will be completed at all visits.

An abbreviated PE will include at minimum general appearance, examination of eyes, skin, cardiovascular and respiratory systems, and an abdominal examination.

7.1.4. Electrocardiogram (ECG)

ECGs (12-lead) will be performed for participants from GBT440-031 who transitioned into this study and received:

- Voxelotor at a dose lower than the selected dose (eg. 900 mg for this trial)
- Placebo

ECGs will be performed after a participant has rested for at least 5 minutes in the seated or supine position. ECGs may be omitted pending a review of ECG data from GBT440-031 or ECG analyses from other clinical studies that indicate ECGs do not need to be collected in this trial. In this case, no study-specific ECGs would be required, but should still be performed as per standard of care.

Analysis from GBT440-0115, a dedicated TQT study in healthy subjects, indicated that voxelotor had no clinically significant ECG findings or no effect on the QT interval; therefore, ECG collection in this trial is no longer required as of 20Aug2019.

7.1.5. Laboratory Assessments

Central laboratory assessments will be performed for participants enrolled in the United States and Europe.

Local laboratory assessments will be performed by each site's local laboratory for participants enrolled outside of the United States or Europe.

The laboratory parameters listed in the sections below will be assessed. Additional laboratory assessments may be collected as indicated per standard of care for clinical management.

For adolescent participants, the total volume of blood collected for will not exceed the recommended blood sample volume limits outlined in 2010 WHO Guidelines. For this study, 12 years of age is the youngest age to be enrolled, thus total blood volume collection will not exceed 2.4 mL/kg in a given 4 week period, for any adolescent enrolled in the study.

7.1.5.1. Hematology (Day 1 through Week 48)

Hematology parameters for this trial are:

- RBC
- hematocrit (Hct)
- Hb
- platelets
- white blood cell (WBC)
- % reticulocytes
- absolute reticulocytes

- RBC distribution width (RDW)
- Mean corpuscular volume (MCV)
- Mean corpuscular hemoglobin concentration (MCHC)

7.1.5.2. Blood Chemistry (Day 1 through Week 48)

Serum chemistry parameters are:

- alanine aminotransferase (ALT)
- alkaline phosphatase (ALK)
- aspartate aminotransferase (AST)
- bicarbonate,
- blood urea nitrogen (BUN)
- creatinine
- lactate dehydrogenase (LDH)
- Sodium
- Potassium
- Bilirubin (total, direct, and indirect)

Assessment of hematology and serum chemistry after Week 48 but should be performed per standard of care.

After Week 48, local laboratory assessments for Hb and measures of hemolysis will be performed by each site's local laboratory for participants enrolled outside of the United States and Europe. (Every 24 weeks)

- Hemoglobin
- % reticulocytes
- absolute reticulocytes
- Bilirubin (total, direct, and indirect)

7.1.5.3. Exploratory Measures Related to SCD Pathophysiology (Day 1, Weeks 12, 24, and 48)

function. CCI damage is a progressive complication of SCD that begins in childhood and may progress CCI. Assessments will be performed only for participants enrolled in the United States and Europe.

• CCI

7.1.5.4. Pregnancy Test (All visits)

Female study participants who have not experienced menarche will not undergo pregnancy testing. Should a female participant experience menarche during the course of the study, the participant will be considered a female of childbearing potential and will undergo pregnancy testing as per the Schedule of Assessments.

Female study participants of childbearing potential will have urine pregnancy tests at all visits. Female study participants with a positive pregnancy test at Day 1 will not be eligible to participate in the study.

If a urine pregnancy test is positive, the result must be confirmed per local standard of care (eg, ultrasound or serum pregnancy test). Female participants of child-bearing potential should be reminded to avoid pregnancy, and all active male participants should be reminded to avoid fathering a child. This discussion should be documented in the participant's medical record.

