15. APPENDICES

Appendix 1. Schedule of assessments

Assessments			Tre	eatment I	Period					End of Studyi
Study Day(s)	Day 1ª	W4* ± 5 days	W8* ± 5 days	W12 ± 5 days	W24 ± 10 days	W36 ± 10 days	W48 ± 10 days	Q12 Wks ± 10 days	Q24 Wks ± 10 days	
Informed Consent/Assent	X							unjs	unjs	
Eligibility Assessment	X									
Medical History	X									
Physical Examination b	X	X	X	X	X		X		X	X
Vital Signs ^c	X	X	X	X	X		X			X
Adverse Events	X	X	X	X	X		X		X	X
Concomitant Medications	X	X	X	X	X		X		X	X
Hematology/Chemistry analyzed by Central Laboratory (US and Europe only) ^d	X	X	X	X	X		X			X
Hematology/Chemistry analyzed by Local Laboratory (ex-US and ex-Europe only) ^{d, e}	Xª	X	X	X	X		X		X f	Х
Exploratory Laboratory CCI (US and Europe Only)	X			X	X		X			
Urine Pregnancy Test ^g	X	X	X	X	X		X		X	X
Drug Dispensing and Accountability ^h	X			X	X	X	X	X	X	Х

Assessments		Treatment Period							End of Studyi	
Study Day(s)	Day	W4*	W8*	W12	W24	W36	W48	Q12	Q24	
	1ª	± 5	± 5	± 5	± 10	± 10	± 10	Wks	Wks	
		days	days	days	days	days	days	± 10	± 10	
								days	days	

Amendment 3

Abbreviations: Q = every; W = week; Wks = weeks

- * Participants from GBT440-031 who received GBT440 900 mg or placebo, or who received voxelotor for less than 12 weeks will have additional assessments at Week 4 and Week 8.
- a. Eligibility assessments will be determined on Day 1 prior to dosing. If labs were done for GBT440-031 or this study within 7 days of Day 1, they do not need to be repeated on Day 1.
- Abbreviated Physical Exam which includes: general appearance, examination of eyes, skin, cardiovascular and respiratory systems, an abdominal examination and a symptom directed examination.
- c. Vital signs (heart rate [HR], blood pressure [BP]) will be collected after a participant has rested for at least 5 minutes in the seated or supine position. A repeated measurement of HR and BP will be taken if the first reading is outside the normal range and deemed clinically significant.
- d. Hematology assessments will include: red blood cell (RBC), hematocrit (Hct), hemoglobin (Hb), platelets, white blood cell (WBC), we reticulocytes, absolute reticulocytes, RBC distribution width (RDW), mean corpuscular volume (MCV) and mean corpuscular hemoglobin concentration (MCHC). After Week 48, hematology assessments should only be performed per standard of care.

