- e. Serum chemistries will include: Alanine aminotransferase (ALT), alkaline phosphatase (ALK), aspartate aminotransferase (AST), bicarbonate, BUN, creatinine, LDH, sodium, potassium, bilirubin (total, direct, and indirect). After Week 48, serum chemistries should only be performed per standard of care.
- f. After Week 48 (for participants enrolled outside of the United States and Europe), laboratory values for measures of hemolysis such as hemoglobin, % reticulocytes, absolute reticulocytes, and bilirubin (total, direct, and indirect) will be collected every 24 weeks.
- g. If a urine pregnancy test is positive, the result must be confirmed per local standard of care (eg. ultrasound or serum pregnancy test).
- h. Voxelotor will be dispensed in 12-week (~90 day) intervals with instruction to participants to return any used/unused bottles to clinic.
- The End of Study (EOS) visit should be conducted within 28-35 days after last dose of study drug for participants who withdraw from the study early.

The EOS visit can occur any time after participants obtains commercial voxelotor for participants who complete study per protocol. Participants who complete study per protocol should remain on study drug until EOS visit is completed.

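### Protocol Section 7.1.5.4 calls for a urine pregnancy test at every visit, but Appendix 1 marks none at Week 36 or in the Q12 Wks column, and the protocol does not say which prevails

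*Protocol*

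**What the plan says.** Protocol Section 7.1.5.4 carries the words for every visit in its heading, and its second paragraph repeats the rule: "Female study participants of childbearing potential will have urine pregnancy tests at all visits". The paragraph before it deals with a participant who reaches menarche on study: "the participant will be considered a female of childbearing potential and will undergo pregnancy testing as per the Schedule of Assessments".

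In Appendix 1 the row "Urine Pregnancy Test" is marked at Day 1, W4, W8, W12, W24, W48, Q24 Wks and End of Study. It is blank at W36 and Q12 Wks. The row "Drug Dispensing and Accountability" is marked in both of those columns. Footnote h to that row reads: "Voxelotor will be dispensed in 12-week (~90 day) intervals with instruction to participants to return any used/unused bottles to clinic". Section 5.2 treats these occasions as visits: "Participants will receive a 3-month (90 day) supply of study drug at each dispensation visit".

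On the background risk, Section 5.6 says "There is no information about effects that voxelotor could have on the development of the fetus in humans", and Section 5.6.1 says "pregnancy should be avoided by either abstinence from sex/sexual intercourse or the use of highly effective means of contraception".

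**The concern.** A site that works from the table will not test at Week 36, Week 60, Week 84 and so on. A site that works from the text will. Both can claim to follow the protocol, and a monitor has no written rule for deciding which one has deviated.

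The stake is participant safety, not inference. Pregnancy is an exclusion criterion (Section 4.2) and a listed reason to stop treatment (Section 4.3), and exposure during pregnancy must be reported within 24 hours of the investigator learning of it (Section 7.3.1). Under the table, a further supply of about 90 days is dispensed midway between two tests without a test on that day. No efficacy endpoint, safety summary or other statistical output in the SAP depends on the answer.

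**Working it through.** The plan states no figure to reproduce. The check has three parts: reading the table by column, looking for a reconciling rule, and counting tests.

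**1. Column reading.** Appendix 1 has ten columns: Day 1, W4, W8, W12, W24, W36, W48, Q12 Wks, Q24 Wks, End of Study.

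| Row | W24 | W36 | W48 | Q12 Wks | Q24 Wks |
|---|---|---|---|---|---|
| Urine pregnancy test | X | blank | X | blank | X |
| Physical examination | X | blank | X | blank | X |
| Adverse events | X | blank | X | blank | X |
| Drug dispensing | X | X | X | X | X |

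The pregnancy test is marked in 8 of the 10 columns. The alignment can be confirmed from the local-laboratory row: its footnote f mark falls in the Q24 Wks column, and footnote f describes collection every 24 weeks.

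**2. Search for a reconciling rule.**
- Section 7.1 sends the timing of safety assessments to Appendix 1. It neither limits the sentence in Section 7.1.5.4 nor gives the table precedence.
- The reference to the Schedule within Section 7.1.5.4 concerns participants who reach menarche on study. The next paragraph states the every-visit rule for all participants of childbearing potential.
- Footnote g to the pregnancy row covers only confirmation of a positive result.
- SAP Section 2.1 lists visits that have assessments: Day 1, Weeks 12, 24 and 48, then every 24 weeks. It does not govern site procedures. The clause in SAP Section 2 that lets the SAP supersede the protocol is about analysis methodology.

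**3. Gaps and counts.** Inputs: 12-weekly dispensing from Day 1 (Appendix 1 and its footnote h) and visit windows of ±10 days from Week 24 on (Appendix 1).

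Longest planned gap from Week 24 = nominal interval + 10 days late + 10 days early:
- Appendix 1: 24 × 7 + 10 + 10 = 168 + 20 = 188 days.
- Text: 12 × 7 + 10 + 10 = 84 + 20 = 104 days.

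Planned tests through week H (H a multiple of 24, at least 48), leaving out W4, W8 and End of Study because they are the same under both readings:
- Text: Day 1 plus every 12 weeks = 1 + H/12.
- Appendix 1: Day 1, W12, then every 24 weeks from W24 = 2 + H/24.
- Difference: H/24 − 1.

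| Through week | Appendix 1 | Text | Extra |
|---|---|---|---|
| 48 | 4 | 5 | 1 |
| 96 | 6 | 9 | 3 |
| 192 | 10 | 17 | 7 |

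Through Week 192 the dispensing visits without a marked test are Weeks 36, 60, 84, 108, 132, 156 and 180.

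**The case against.** The best reply is that no conflict was intended. At W36 and Q12 Wks dispensing is the only thing marked. Section 7.1.3 asks for a physical examination at every visit and Section 7.2 asks for adverse event assessment at each one, yet both rows are blank in the same two columns. That looks like a consistent habit of writing visit to mean assessment visit. SAP Section 2.1 lists visits in the same way. The neighbouring laboratory headings end at Week 48, so the heading of Section 7.1.5.4 may only mean that pregnancy testing continues beyond that point. A blank cell is also the normal way for a schedule to show that something is not done.

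Much of this stands, and it makes the dispensing-only reading the more natural one. It does not turn that reading into a rule. Section 7.1.5.4 has no limiting words, Section 5.2 calls the dispensing occasions visits, and footnote h has participants returning bottles to the clinic.

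Two further replies concern importance. Highly effective contraception or abstinence is required, Section 7.1.5.4 asks for documented reminders, and Section 7.1 lets the investigator assess more often where needed. These stand and keep the point minor. The current protocol was approved in January 2024, while the study was already under way before ECG collection was dropped in August 2019, so few participants may still have a Week 36 visit ahead of them. That is a fair caution, but the documents do not give the remaining follow-up.

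A reader might infer that the protocol requires 12-weekly testing and that Appendix 1 wrongly leaves it out. The documents do not establish which interval was meant, so that goes too far.

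**Conclusion.** The text and the schedule disagree at W36 and at the 12-weekly dispensing visits between the 24-weekly visits, and nothing in the protocol settles the disagreement. It is a minor inconsistency in a safety procedure, with no effect on any endpoint or analysis.

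Its size is a factor of two in the planned testing interval from Week 24. That factor applies only if the text is read literally. The 188 and 104 days are the longest gaps between planned tests when both visits fall at the edges of their windows. A reader might take them as durations of undetected fetal exposure. They are not: the documents give no pregnancy rate, and the contraception requirements act against such events. The horizons in the count are illustrative because the study has no fixed duration. Confidence is high that the two places differ and only moderate on what was intended.

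**What to change.** **Preferred change.** In the urine pregnancy test row of Appendix 1, mark W36 and Q12 Wks. Every 12-weekly dispensing visit then carries the test that Section 7.1.5.4 describes, and the planned gap from Week 24 falls from 24 to 12 weeks.

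**Cost.** For each participant of childbearing potential, one extra urine test at Week 36 and one every 24 weeks after Week 48 while she remains on study, all at visits already scheduled for dispensing. It also needs a one-row edit at the next amendment, with the IRB/EC approval that Section 11.1 requires. The benefit depends on how much follow-up remains. This change settles pregnancy testing only; the same loose wording in Sections 7.1.3 and 7.2 would still need tidying.

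**Alternative.** If the sponsor confirms that 24-weekly testing was intended, reword Section 7.1.5.4 (heading and text), and likewise Sections 7.1.3 and 7.2, to refer to the visits marked in Appendix 1. This removes the conflict and adds no tests, but it keeps the longer gap.
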